
 Removal of all STGG (Skim Milk-Tryptone-Glucose-Glycerol) wording throughout the protocol. STGG product not being available, it has been decided to replace it with cryobeads for storage of bacterial isolates. PCR testing on samples stored in cryobeads was shown to be as efficient as for samples stored in STGG. Besides, this decision has been taken for alignment with other COPD studies, where STGG solutions are no longer used. Clarification of technique used for target identification. For the primary endpoint, various viral pathogens will be identified but not quantified. Along this line, the wording “and by HRV quantitative RT-PCR” has been removed from primary endpoint to avoid confusion as HRV viral load data will be reported as part of the tertiary endpoints. Clarification in exclusion criteria section (4.3). Administration of antibiotics before study entry, where study entry is meant to be Visit 1. Clarification in study procedure section (6.3) and in the section for recording current medication (6.4.2.10) during scheduled visits, where it has been specified that recording of any current medication is applicable for any disease not only COPD-related. Moreover, a footnote referring to Table 10 “Reporting period for SAE and AEs leading to withdrawal” has been added for further clarification, both in Table 4 and 5. Addition of a section (actual 6.4.2.6) for Pregnancy test for Visit 1, Visit 2 and Visit 3. A Pregnancy test section for Screening Visit was included during Protocol Amendment 1: to be consistent, same wording has been included for the subsequent visits. 	

- Clarification of reporting of severe AECOPDs. Two sentences have been added in sections 7.1.1 and 7.2.2.1 for making clear that severe AECOPD events are not to be reported as SAE as they are meant as disease-related outcomes.
- Rewording in the table concerning reporting period for SAE and AEs leading to withdrawal for better clarification (Table 10).
- Addition of a new outsourced laboratory (DDL).
- To correct some typographical errors.

Amended text has been included in *bold italics* and deleted text in ~~strikethrough~~ in the following sections:

List of Abbreviations

STGG

~~Skim Milk-Tryptone-Glucose-Glycerol~~

Section 4.3 Exclusion criteria for enrolment

- Administration of antibiotics within 1 month of study entry OR continuous administration of antibiotics (defined as more than 30 days in total) within 90 days before study entry.
* Study entry is Visit 1. If this exclusion criteria is met during Screening Visit the patient can enter the study and this exclusion criteria will be reassessed during Visit 1.

Section 6.3 Outline of study procedures

Table 4 List of study procedures for scheduled visits

Epoch	Type of contact	Epoch 001			
		Screening Visit	Visit 1	Visit 2	Visit 3
Time point		Pre-Month 0	Month 0	Month 6	Month 12
Informed consent ^a		●			
Check inclusion/exclusion criteria ^a		●	○		
Record demographic data ^a		●			
Record medical history		●			
Record history of AECOPD within the previous year ^b		●			
Record intercurrent comorbidities ^c		○	●	●	●
Record history of pneumococcal and influenza vaccination		○	●	●	●
Smoking exposure history (ATS-DLD-78A questionnaire)/ biomass exposure history (Biomass Exposure questionnaire)		○			
Smoking status		●	●	●	●
Physical examination including vital signs ^h		●	○	○	○
Urine Pregnancy Test		●	●	●	●
Measure/ record height and weight ^d		●			●
Pre- and post-bronchodilator spirometry ^e		●			●
Chest X-ray ^f		●			
Record subject's COPD status (stable, recovered or not recovered)			●	●	●
Record current medication for COPD			●	●	●
Record healthcare resource utilisation			●	●	●
Record additional treatments prescribed by primary and secondary care physicians			●	●	●
Train subject on use of electronic Diary Card and assign electronic Diary Card to the subject		○	○		
Return electronic Diary Card					○
Sputum sampling ^g		●	●	●	●
Blood samples for biomarkers			●		●
Record Adverse Events (AEs)* ^h related to study participation		●	●	●	●
Record serious adverse events (SAEs) ^h related to study participation		●	●	●	●
Screening conclusion		●			
Study conclusion					●
HRQOL questionnaires:					
CAT			○	○	○
SGRQ-C			○	○	○

^a Refer to Table 10 for description of which AE/SAEs are collected in this study.^b Physical examination (Visit1-3) should be done only if necessary by the investigator or delegate.

Table 5 List of study procedures for AECOPD visits

Type of contact	AECOPD Visit	End of AECOPD phone call(s)
Time point	within 96 hours of onset symptoms	at least every 2 weeks as of AECOPD visit until AECOPD has resolved ⁱ
Record date of visit	•	
Physical examination ^j	•	
Urine Pregnancy Test	•	
Chest X-rays/pneumonia confirmation ^j	•	
Confirm AECOPD and record its start date	•	
Record current medication for AECOPD	•	
Record healthcare resource utilisation	•	
Record additional COPD treatments prescribed by primary and secondary care physicians		•
Sputum sampling ^k	•	
HRQOL questionnaire:		
CAT	0	
Record AECOPD severity ^m	•	•
Record AECOPD end date		•
Record Adverse Events (AEs) ^{*^} related to study participation	•	•
Record serious adverse events (SAEs) [^] related to study participation	•	•

ⁱ Refer to Table 10 for description of which AE/SAEs are collected in this study.

Section 6.4 Detailed description of study procedure

Sputum sampling at sub-sections 6.4.1.14 – 6.4.2.15 – 6.4.3.9:

Remaining DTT-sputum will be aliquoted as such and/or further diluted in STGG. These samples will be kept at -70/80°C until shipment to GSK or GSK designated lab for testing.

Section 6.4.2.6 Pregnancy test

Female subjects of childbearing potential are to have a urine pregnancy test prior to any study procedure. Note: The urine pregnancy test must be performed even if the subject is menstruating at the time of the study visit.

Section 6.4.2.10 Record current medication for COPD

- At each study visit/contact, the investigator should question the subject about any medications taken. ~~administered for treatment of COPD.~~
- All medications administered ~~for treatment of COPD~~ will be recorded in the eCRF.

Section 6.5.3 Laboratory assays

Table 8 Microbiology

Further bacterial pathogens identification

Viral pathogens identification

System	Component	Method	Scale	Laboratory
Quality assessment				
Fresh sputum	Please refer to SPM and/or Central Laboratory Manual for components tested	Gram staining	Qualitative/ semi-quantitative	Investigator institution or GSK designated laboratory
Bacterial pathogen identification				
Fresh sputum	Respiratory bacterial pathogens (including H. influenzae , S. pneumoniae , M. catarrhalis , S. aureus , P. aeruginosa , K. pneumoniae and A. baumannii)	Standard bacteriological culture and standard identification methods including semi-quantitative culture	Qualitative	Investigator's institution and/or at a laboratory designated by GSK Biologicals
			Semi-quantitative	
H. influenzae isolates of positive H. influenzae culture plates	H. influenzae species confirmation and when possible Hi/NTHi differentiation Sample collection for potential further characterisation	Molecular techniques such as differentiation PCR	Qualitative	GSK Biologicals laboratory* or designated laboratory
Stored sputum	Respiratory bacterial pathogens (including H. influenzae , S. pneumoniae , M. catarrhalis , S. aureus and P. aeruginosa , Streptococcus pyogenes))	Multiplex PCR	Qualitative and/ or quantitative	GSK Biologicals laboratory * or designated laboratory
Viral pathogen identification				
Stored sputum	Respiratory viral pathogens (including RSV, parainfluenza virus, enterovirus/ HRV, metapneumovirus, influenza virus, adenovirus, bocavirus and coronavirus)	Multiplex-PCR	Qualitative	GSK Biologicals laboratory * or designated laboratory
	Respiratory viral pathogens (such as HRV)	RT-PCR	Quantitative	GSK Biologicals laboratory* or designated laboratory

Stored frozen sputum samples (in DTT supplemented with skim milk, tryptone, glucose, and glycerine [STGG] medium) might be collected when possible for potential assay development/validation purpose.

Synopsis Primary endpoints and Section 9.1.1 Primary endpoint

- Occurrence of potential bacterial and viral pathogens in sputum of stable COPD patients and during AECOPD, over the course of 1 year:
 - Bacterial pathogens, as identified by bacteriological methods, including (but not necessarily limited to) *H. influenzae*, *M. catarrhalis*, *S. pneumoniae*, *S. aureus*, *P. aeruginosa*, *K. pneumoniae* and *A. baumannii*.
 - Viral pathogens, as identified by RT PCR, including (but not necessarily limited to) RSV, parainfluenza virus, enterovirus/ Human Rhinovirus (HRV), metapneumovirus, influenza virus, adenovirus, bocavirus and coronavirus ~~and by HRV quantitative RT PCR~~.

Section 7.1.1 Definition of an adverse event

An AE is any untoward medical occurrence in a subject, temporally associated with the use of a medicinal product, whether or not considered related to the medicinal product, or temporally associated with a study procedure.

Examples of an AE include

- Signs, symptoms, or the clinical sequelae of a suspected interaction.

Examples of an AE DO NOT include:

- Medical or surgical procedures (e.g., endoscopy, appendectomy); the condition that leads to the procedure is an AE.
- Situations where an untoward medical occurrence did not occur (e.g., social and/or convenience admission to a hospital, admission for routine examination).
- Anticipated day-to-day fluctuations of pre-existing disease(s) or condition(s) present or detected at the start of the study that do not worsen.
- *Occurrence of a severe AECOPD, unless in the opinion of the Investigator this is related to study procedure.*

Section 7.2.1 Time periods for detecting and recording AEs and SAEs – Table 10

Study activity	Screening Visit	Visit 1	Visit 2	Visit 3	AECOPD Visit	Study Conclusion
	Pre-Month 0	M 0	M 6	M 12	Within 96 hours of onset symptoms	
AEs/SAEs related to study participation*						
AEs/SAEs leading to withdrawal from the study						

Section 7.2.2.1 Active questioning to detect SAEs

Each subject/ will be instructed to contact the investigator immediately should the subject manifest any signs and symptoms (s)he perceives/ they perceive as serious. ***However, an occurrence of severe AECOPD is not defined as an SAE and therefore does not need to be reported as such, unless in the opinion of the Investigator this is related to a study procedure.***

12.3.	Time between 2 e-diary signals for exacerbations/evaluation of baseline symptom score:	44
12.4.	Definition of Missed AECOPD visits.....	44
12.5.	Unconfirmed AECOPD event with morning e-diary signal alert notification.	44

CONFIDENTIAL

201112 (EPI-NTHI-001 BOD APA)

Statistical Analysis Plan Amendment 2 Final

12.6. Grading of severity of an exacerbation.....	45
13. ANNEX 3: STUDY SPECIFIC MOCK TFL.....	45

CONFIDENTIAL201112 (EPI-NTHI-001 BOD APA)
Statistical Analysis Plan Amendment 2 Final**LIST OF TABLES**

	PAGE
Table 1 COPD severity stages included in the study.....	37

CONFIDENTIAL

201112 (EPI-NTHI-001 BOD APA)
Statistical Analysis Plan Amendment 2 Final

LIST OF FIGURES

	PAGE
Figure 1 Workflow of study assessment for AECOPD	28

CONFIDENTIAL

201112 (EPI-NTHI-001 BOD APA)
 Statistical Analysis Plan Amendment 2 Final

LIST OF ABBREVIATIONS

A. baumannii	Acinetobacter baumannii
AE	Adverse event
AECOPD	Acute exacerbation of COPD
CAT	COPD assessment test
CI	Confidence Interval
COPD	Chronic Obstructive Pulmonary Disease
CRF	Case Report Form
EXACT-PRO	Exacerbations of Chronic Pulmonary Disease Tool - Patient Reported Outcome
FAS	Full Analysis Set
FEV ₁	Forced expiratory volume in 1 second
GOLD	Global Initiative for Chronic Obstructive Lung Disease
GSK	GlaxoSmithKline
H. haemolyticus	Haemophilus haemolyticus
H. influenzae	Haemophilus influenzae
HRQOL	Health-related quality of life
HRV	Human rhinoviruses
K. pneumoniae	Klebsiella pneumoniae
LL	Lower Limit of the confidence interval
M. catarrhalis	Moraxella catarrhalis
MA	Main Analyses
MedDRA	Medical Dictionary for Regulatory Activities
NTHi	Non-Typeable Haemophilus influenzae
P. aeruginosa	Pseudomonas aeruginosa
PCR	Polymerase chain reaction

CONFIDENTIAL201112 (EPI-NTHI-001 BOD APA)
Statistical Analysis Plan Amendment 2 Final

PEF	Peak Expiratory Flow
RSV	Respiratoir Syncytial Virus
RT-PCR	Real-time polymerase chain reaction
SAE	Serious adverse event
S. aureus	Staphylococcus aureus
SAP	Statistical Analysis Plan
SD	Standard Deviation
SGRQ-C	St. George's Respiratory Questionnaire for COPD patients
S. pneumoniae	Streptococcus pneumoniae
SR	Study Report
TFL	Tables Figures and Listing template annexed to SAP
UL	Upper Limit of the confidence interval

CONFIDENTIAL201112 (EPI-NTHI-001 BOD APA)
Statistical Analysis Plan Amendment 2 Final**1. DOCUMENT HISTORY**

Date	Description	Protocol Version
28-JUL-2017	Version 1	Protocol Amendment 1 13-FEB-2017
14-SEPT-2018	SAP Amendment 1 Updates done before Interim Analysis: - analysis population was adapted to Protocol Amendment 2 - elimination codes were aligned to PDMP v.4 - analyses added to Interim Analysis timepoint - sputum quality - alignment with the protocol/CRF - more details about laboratory methods were added - several minor corrections	Protocol Amendment 2 19-OCT-2017
05-AUG-2020	SAP Amendment 2 Updated made before final analysis: - elimination codes were aligned to PDMP v.9 - Statistical modelling details added or updated based on preliminary analyses results - Addition, removal or update of a few new analyses related to secondary (incidence rate) and tertiary objectives as per team's request - some general minor edits were implemented	Protocol Amendment 2 19-OCT-2017

2. STUDY DESIGN

Type of design: epidemiological, prospective, interventional, multi-country, cohort study. The study targets enrolling approximately 200 stable moderate to very severe COPD patients, males and females, aged 40 years or older at the time of enrolment, with at least 1 documented moderate or severe AECOPD in the year before enrolment.

This study will be conducted in several sites among several countries in Asia Pacific [Hong Kong, Philippines, Korea, Taiwan].

Type of study: self-contained.

Duration of the study: approximately 1 year for each patient.

Study visits/contacts:

- Screening visit
- Three scheduled visits occurring at 6 months intervals.
- For each AECOPD: AECOPD visit (within 96 hours of the onset of the symptoms) and follow-up phone call(s) (at least every 2 weeks until the AECOPD has resolved). Follow-up phone contacts will define end of AECOPD.

CONFIDENTIAL

201112 (EPI-NTHI-001 BOD APA)
Statistical Analysis Plan Amendment 2 Final

The following group names will be used for the statistical analyses:

Group order in tables	Group label in tables	Group definition for footnote
1	COPD	Patients with moderate to very severe COPD

CONFIDENTIAL201112 (EPI-NTHI-001 BOD APA)
Statistical Analysis Plan Amendment 2 Final

3. OBJECTIVES

3.1. Primary objective

To estimate the proportion of potential bacterial and viral pathogens (overall and by species) detected in sputum of stable COPD patients and during AECOPD, using respectively bacteriological methods and viral PCR, over the course of 1 year.

3.2. Secondary objectives

- To evaluate the concordance between PCR and bacteriological methods data in sputum for potential bacterial pathogens.
- To estimate the proportion of potential bacterial and viral pathogens (overall and by species) detected in sputum of stable COPD patients, by GOLD grade.
- To estimate the proportion of potential bacterial and viral pathogens (overall and by species) detected in sputum during AECOPD, by severity of AECOPD.
- To estimate the incidence rate of all-cause AECOPD, overall and by GOLD grade.
- To describe the severity and duration of all-cause AECOPD, overall and by GOLD grade.
- To assess the impact of all-cause AECOPD on HRQOL.
- To assess the impact of all-cause AECOPD on lung function.
- To assess the impact of all-cause AECOPD on healthcare utilisation.

3.3. Tertiary objectives

- To assess the use of EXACT-PRO for determining the end date of AECOPD.
- To evaluate the load of bacterial and viral pathogens in stable COPD and during AECOPD.
- To collect biological specimens for future respiratory disease-related testing:
 - Aliquots of sputum samples for assay development and microbiome analysis at stable visits and during exacerbation.
 - Blood sampling for potential biomarkers for identification/quantification of biomarkers at Visit 1 and Visit 3.

CONFIDENTIAL

201112 (EPI-NTHI-001 BOD APA)
 Statistical Analysis Plan Amendment 2 Final

4. ENDPOINTS

4.1. Primary endpoint

- Occurrence of potential bacterial and viral pathogens in sputum of stable COPD patients and during AECOPD, over the course of 1 year:
 - Bacterial pathogens, as identified by bacteriological methods (culture), including (but not necessarily limited to) *H. influenzae*, *M. catarrhalis*, *S. pneumoniae*, *S. aureus*, *P. aeruginosa*, *K. pneumoniae* and *A. baumannii*.
 - Viral pathogens, as identified by PCR, including (but not necessarily limited to) RSV, parainfluenza virus, enterovirus/ HRV, metapneumovirus, influenza virus, adenovirus, bocavirus and coronavirus.

4.2. Secondary endpoints

- Occurrence of potential bacterial pathogens in sputum of stable COPD patients and during AECOPD, as measured by real-time qualitative PCR/ quantitative PCR and compared to data from bacteriological methods, over the course of 1 year:
 - Including (but not necessarily limited to) *H. influenzae*, *M. catarrhalis*, *S. pneumoniae*, *S. aureus* and *P. aeruginosa*.
- Occurrence of potential bacterial and viral pathogens (overall and by species) in sputum of stable COPD patients by GOLD grade, over the course of 1 year.
- Occurrence of potential bacterial and viral pathogens (overall and by species) in sputum during AECOPD by severity of AECOPD, over the course of 1 year.
- Incidence rate (per patient per year) of AECOPD, overall and by GOLD grade, over the course of 1 year.
- Severity of AECOPD, overall and by GOLD grade, over the course of 1 year.
- Duration of AECOPD, overall and by AECOPD severity, over the course of 1 year.
- CAT score in stable COPD patients and during AECOPD, over the course of 1 year.
- SGRQ-C score in stable COPD patients, over the course of 1 year.
- FEV₁% of predicted normal value in stable COPD patients, at Pre-Month 0 and Month 12.
- Healthcare utilisation, over the course of 1 year.

4.3. Tertiary endpoints

- EXACT-PRO scores in stable COPD patients and during AECOPD, over the course of 1 year.
- Bacterial load measured by both culture and PCR at stable and exacerbation visits.
- HRV load measured by PCR at stable and exacerbation visits.

CONFIDENTIAL201112 (EPI-NTHI-001 BOD APA)
Statistical Analysis Plan Amendment 2 Final

5. ANALYSIS SETS

The following data sets will be defined.

5.1. All screened set

The all screened set will include all patients that were evaluated for enrolment and that signed the informed consent. Patients with invalid informed consent or fraud data will be excluded from the all screened set.

5.2. All enrolled set

The all enrolled set will include patients from the all screened set minus those that were screening failures.

5.3. Full Analysis Set

The Full Analysis Set (FAS) will include patients from the all enrolled set except for those who discontinued the study at Visit 1.

Study objectives will be assessed on the FAS. The population set for each analysis will change according to the subjects evaluable for the specific endpoint.

5.3.1. Change in analysis population from protocol amendment 2

The analysis population is aligned with protocol amendment 2.

5.4. Criteria for eliminating data from the Analysis Sets

Details about elimination codes used to identify patients to be eliminated from analysis are provided below for each set.

5.4.1. Elimination from All Screened Set

Code 800 (fraudulent data) and code 900 (invalid informed consent) will be used for identifying patients eliminated from All Screened Set.

5.4.2. Elimination from All Enrolled Set

Code 800 (fraudulent data), code 900 (invalid informed consent) and code 2010 (Protocol violation - inclusion/exclusion criteria) will be used for identifying patients eliminated from All Enrolled Set.

CONFIDENTIAL

201112 (EPI-NTHI-001 BOD APA)
 Statistical Analysis Plan Amendment 2 Final

5.4.3. Elimination from the Full Analysis Sets (FAS)

Code 800 (fraudulent data), code 900 (invalid informed consent) and code 2010 (Protocol violation - inclusion/exclusion criteria) will be used for identifying patients eliminated from FAS.

Of note, the only difference between the All Enrolled Set and the FAS comes from patients that withdraw from the study at visit 1. These patients will be in the All Enrolled Set but will not be in the FAS. However, this is not a protocol deviation and is not mentioned in this section.

5.4.4. Elimination codes details

A list of reasons for elimination from the analyses (interim analysis and final analysis), is reported below:

Code	Condition under which the code is used
800	Fraudulent data
900	
 1. Informed consent deviations 
 1.a. Signed informed consent not available on site 1.b. Wrong informed consent version signed 1.c. Informed consent not signed and/or dated by subject 1.d. Informed consent not signed and/or dated by appropriated site staff 1.e. Informed consent not signed prior to any study procedure 1.f. Other informed consent deviations 2. Eligibility deviations 
 2.a. Biological sample specimen procedures 
 2.a.a. PII recorded in label of sample
2010	
 1. Eligibility criteria not met
2040	
 1. Excluded medication, vaccine, or device 
 1.a. Prohibited medication as per protocol (e.g., antibiotics administration will impact the primary endpoint)

CONFIDENTIAL201112 (EPI-NTHI-001 BOD APA)
Statistical Analysis Plan Amendment 2 Final

Code	Condition under which the code is used
2050	
 1. Not withdrawn after developing withdrawal criteria 
 1.a. Not withdrawn after developing withdrawal criteria other than prohibited vaccination/medication
2090	
 1. Assessment or time point completion 
 1.a. Out of window visit (assessment) for efficacy 
 1.a.a. Sputum sample collection outside the 96 hour-interval since exacerbation onset
2100	
 1. Study procedures 
 1.a. Biological sample specimen procedures 
 1.a.a. Low volume (not sufficient to perform testing) 1.a.b. Mislabeled (sample not tested)
2110	
 1. Study procedures 
 1.a. Biological sample specimen procedures 
 1.a.a. Incorrect or expired sample tube used 1.a.b. Incorrect spinning/processing of sample
2120	
 1. Assessment or time point completion 
 1.a. Other assessment not properly performed 
 1.a.a. Sputum culture not completed within six hours, 1.a.b. Culture: error in testing algorithm for identification (vs AP, eg.no optochin for Strep.) 1.b. Assessmet not properly performed 
 1.b.a. Sputum processing priorities not respected. 1.b.b. Frozen sputum DTT before culture

CONFIDENTIAL201112 (EPI-NTHI-001 BOD APA)
Statistical Analysis Plan Amendment 2 Final

Code	Condition under which the code is used
	
1.b.c. Sputum DTT aliquots not frozen <6hrs
 
1.b.d. Sputum not diluted after glass smear preparation
 
1.b.e. Sputum diluted with concentrated DTT
 
1.b.f. Gram stain not read on the same day as preparation (not an issue if still done < 10 days)
 
1.b.g. Sputum glass smear for quality not prepared or assessment not performed
 
2. Study procedures
 
2.a. Biological sample specimen procedures
 
2.a.a. Central/internal/external lab deviations,
 
2.a.b. Mislabelling (sample tested),
 
2.a.c. Wrong packaging that impacts quality of the sample (i.e. room temperature packaging for shipping frozen ELISA samples).
 
2.a.d. Temperature log not maintained as required or not tracked
 
2.a.e. "Blood" or Sputum temperature deviations from range defined in protocol and/or SPM/lab manual - room temperature and freezer -70°C
 
2.a.e.a. Sputum storage (only if not tested on same day), then storage cooled (+2-8°C): no impact if < 24hrs. If > 24hrs but still <72hrs, potential impact, to evaluate case by case. If >72hrs, elimination
 
2.a.e.b. Sputum DTT (-70°C): range +/-20°C. Lab is looking for additional stability data. Normally, ok at -20°C for 1 month (for PCR)
 
2.a.f. Sputum collection procedure not following process outlined in the protocol (e.g. sputum collected at home for stable visit)

CONFIDENTIAL

201112 (EPI-NTHI-001 BOD APA)
 Statistical Analysis Plan Amendment 2 Final

Code	Condition under which the code is used
2120a	1. Study procedures 1.a. Biological sample specimen procedures 1.a.a. "Blood" or Sputum temperature deviations from range defined in protocol and/or SPM/lab manual - room temperature and freezer -70°C 1.a.a.a. Sputum DTT - Only culture samples affected
2120b	1. Study procedures 1.a. Biological sample specimen procedures 1.a.a. "Blood" or Sputum temperature deviations from range defined in protocol and/or SPM/lab manual - room temperature and freezer -70°C 1.a.a.a. Sputum DTT - Only PCR samples affected
2120c	1. Study procedures 1.a. Biological sample specimen procedures 1.a.a. "Blood" or Sputum temperature deviations from range defined in protocol and/or SPM/lab manual - room temperature and freezer -70°C 1.a.a.a. Sputum DTT - Only Microbiome samples affected
2120d	1. Study procedures 1.a. Biological sample specimen procedures 1.a.a. "Blood" or Sputum temperature deviations from range defined in protocol and/or SPM/lab manual - room temperature and freezer -70°C 1.a.a.a. Sputum DTT - Only Fibrinogen samples affected

CONFIDENTIAL

201112 (EPI-NTHI-001 BOD APA)
 Statistical Analysis Plan Amendment 2 Final

Code	Condition under which the code is used
2120e	
 1. Study procedures 1.a. Biological sample specimen procedures 1.a.a. "Blood" or Sputum temperature deviations from range defined in protocol and/or SPM/lab manual - room temperature and freezer -70°C 1.a.a.a. Sputum DTT - Only hsCRP samples affected
2120f	
 1. Study procedures 1.a. Biological sample specimen procedures 1.a.a. "Blood" or Sputum temperature deviations from range defined in protocol and/or SPM/lab manual - room temperature and freezer -70°C 1.a.a.a. Sputum DTT - Only CXCL10 samples affected
2120g	
 1. Study procedures 1.a. Biological sample specimen procedures 1.a.a. "Blood" or Sputum temperature deviations from range defined in protocol and/or SPM/lab manual - room temperature and freezer -70°C 1.a.a.a. Blood - Only "other biomarker" samples affected
2120h	
 1. Study procedures 1.a. Biological sample specimen procedures 1.a.a. "Blood" or Sputum temperature deviations from range defined in protocol and/or SPM/lab manual - room temperature and freezer -70°C 1.a.a.a. Blood - Only samples for hematology profile affected

CONFIDENTIAL201112 (EPI-NTHI-001 BOD APA)
Statistical Analysis Plan Amendment 2 Final

Code	Condition under which the code is used
2130	1. Study procedures 1.a. Biological sample specimen procedures 1.a.a. Testing performed on samples not aligned with ICF, 1.a.b. Subjects bled but not supposed to be bled
2500	1. Assessment or time point completion 1.a. Incorrect assessment performed 1.a.a. Other
2600	1. Other 1.a. Other 1.a.a. Any other GCP non-compliance

Code 2040 and codes from 2090 to 2600 are protocol deviations not leading to elimination from the population sets above mentioned but that may lead, judged case by case, to sample elimination from a specific statistical analysis.

CONFIDENTIAL201112 (EPI-NTHI-001 BOD APA)
Statistical Analysis Plan Amendment 2 Final

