9.3.3. Full Analysis Set

The Full Analysis Set (FAS) will include all enrolled patients except for those who discontinued the study during Visit 1.

Study objectives will be assessed on the FAS. The population set for each analysis will change according to the subjects evaluable for the specific endpoint.

Note: Subjects using antibiotics on a continual basis (defined as more than 1 month in total) will be allowed to continue study participation, but may be eliminated from the analyses.

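### SAP code 900, described as invalid informed consent, also covers personal data on a sample label, so as written a labelling error removes a validly consented patient from all three analysis sets

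*SAP*

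**What the plan says.** SAP 5.4.4 introduces its code table with "A list of reasons for elimination from the analyses (interim analysis and final analysis), is reported below". Code 900 has two branches in that table. The first lists consent deviations. The second is headed as eligibility deviations and contains one entry, a sample-procedure item: "2.a.a. PII recorded in label of sample".

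The three preceding subsections give code 900 its effect, each at patient level:

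- SAP 5.4.1: "Code 800 (fraudulent data) and code 900 (invalid informed consent) will be used for identifying patients eliminated from All Screened Set".
- SAP 5.4.2: "code 900 (invalid informed consent) and code 2010 (Protocol violation - inclusion/exclusion criteria) will be used for identifying patients eliminated from All Enrolled Set", alongside code 800.
- SAP 5.4.3: the same three codes "will be used for identifying patients eliminated from FAS".

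The sentence closing SAP 5.4.4 says that code 2040 and codes 2090 to 2600 do not remove anyone from these sets. They may lead, case by case, to a sample being dropped from a particular analysis. Code 900 is outside that range. SAP 5.1 names only invalid consent and fraud as grounds for exclusion from the All Screened Set.

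**The concern.** The label given to code 900 and its contents disagree. Personally identifiable information on a tube is a privacy and sample-handling fault by site staff. It does not show that the patient failed to consent, was ineligible, or gave a false result. Yet the SAP attaches to it the heaviest consequence it has.

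The patient would lose every culture and PCR result, all diary and questionnaire data, spirometry, exacerbation counts and up to about one year of follow-up. SAP 6.2, 6.3, 6.4 and 6.5 all run on the FAS, so primary, secondary, tertiary and safety summaries are all affected. Because removal starts at the All Screened Set, the patient would also be missing from the disposition counts planned in SAP section 6, and the loss would not be visible there.

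**Working it through.** This is a question of rules, so the main check sets the provisions side by side.

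| Fault | Code | Consequence in the SAP |
|---|---|---|
| Personal data on a sample label | 900 | Patient removed from all three sets (5.4.1 to 5.4.3) |
| Sample mislabelled, not tested | 2100 | At most the sample, case by case |
| Sample mislabelled but tested: "2.a.b. Mislabelling (sample tested" | 2120 | At most the sample, case by case |
| Testing not in line with the consent form | 2130 | At most the sample, case by case |

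Three observations follow.

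1. The row fits neither description of code 900. SAP 5.1 and 5.4.1 to 5.4.3 speak of consent (and, separately, fraud).
2. The row does not fit its own parent heading. Eligibility failures have their own code, 2010, and no criterion in protocol 4.2 or 4.3 concerns labels. Protocol 6.5 treats coded labelling as a matter of sample handling.
3. Code 2130, which does touch consent, stays at sample level. A label fault is therefore treated more severely than a departure from the consent form.

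**Size.** The documents do not say how many patients are affected, so the number removed, k, is an assumption shown over a range.

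Inputs: about 200 enrolled (protocol 4.1); 90% participating, one exacerbation visit on average, and 80% giving an evaluable sample (protocol 9.2); three scheduled stable visits (SAP section 2).

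Exacerbation samples per enrolled patient: 0.90 × 1 × 0.80 = 0.72. For 200 patients this gives 200 × 0.72 = 144, against the protocol's figure of around 140.

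The interval is the exact (Clopper-Pearson) one: lower limit = 2.5th percentile of Beta(x, n − x + 1); upper limit = 97.5th percentile of Beta(x + 1, n − x). With n = 140 and x = 42 (30%) it gives 22.6 to 38.3, which reproduces protocol Table 12.

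For the scenarios, n = (200 − k) × 0.72, rounded, and x = 0.30n, left unrounded so that the widths are comparable. Widths are taken from unrounded limits.

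| k removed | Stable samples lost, up to 3k | Exacerbation samples lost, 0.72k | n left | 95% CI at 30% | Width (points) |
|---|---|---|---|---|---|
| 0 | 0 | 0 | 144 | 22.7 to 38.2 | 15.5 |
| 1 | 3 | 0.7 (about 1) | 143 | 22.6 to 38.2 | 15.6 |
| 5 | 15 | 3.6 (about 4) | 140 | 22.6 to 38.3 | 15.8 |
| 10 | 30 | 7.2 (about 7) | 137 | 22.5 to 38.4 | 15.9 |
| 20 | 60 | 14.4 (about 14) | 130 | 22.3 to 38.7 | 16.4 |

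Even with 20/200 = 10% of the cohort removed, the interval widens by 16.4 − 15.5 = 0.9 points.

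**The case against.** The strongest reply is that this is a misfiled table row, not an intended rule. The text of SAP 5.1 and 5.4.1 to 5.4.3 points to consent only. The codes were aligned to a PDMP (version 9, per SAP section 1) that is not among the documents and may limit when the row applies. This stands as a caution: it is not certain that any patient would be removed. But nothing in the SAP says the row is to be read narrowly, and a prespecified plan should not rely on that.

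A second reply is that a privacy breach may touch consent terms, since protocol 6.5 requires testing to respect each subject's consent. Code 2130 answers this: the SAP already handles testing outside the consent form at sample level.

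A third is that the protocol does contemplate excluding a subject over sample handling. Protocol 6.5.1 allows it when supplied collection materials are not used. That is true, but the provision concerns materials and says nothing of labels. The protocol's own definition, "The Full Analysis Set (FAS) will include all enrolled patients except for those who discontinued the study during Visit 1", contains no labelling exclusion. Its silence carries limited weight, because it names no consent or fraud exclusion either.

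A fourth is that all analyses are descriptive (SAP section 7) and the trigger may never occur. That stands, and it limits the importance of the point.

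A reader might go further and infer that losses would cluster by site and so distort the country tables or the pathogen mix. Clustering is possible, because labelling is done by sites. The documents give no count of label errors and no distribution of them. Bias would also need the removed patients to differ from those kept, or country weights to shift materially. Neither is shown.

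**Conclusion.** The inconsistency is real and is in the current SAP (Amendment 2). As written, one label error takes a validly consented patient out of every analysis set. This is at odds with the SAP's own description of code 900 and with how it treats comparable faults.

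The practical size is unknown and probably modest. Over the assumed range of 1 to 20 patients removed, the 95% interval at 30% widens by 0.1 to 0.9 points. The case for change is that valid data would be discarded for a reason unrelated to consent or eligibility; it is not a loss of precision. The range rests on protocol 9.2's 90%, one visit and 80%, on 200 enrolled, and on hypothetical values of k.

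A reader might also infer that serious events would go unreported. The documents do not support that. There is no separate safety set, and what is lost is the patient's place in the FAS-based descriptive summary of SAP 6.5. Expedited SAE reporting under protocol 7.3 is unaffected.

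**What to change.** Move the row on personal data in a sample label from code 900 to code 2120, beside mislabelling. The sentence closing SAP 5.4.4 then makes it a sample-level decision, case by case. Keep code 900 for consent deviations only, so that it matches SAP 5.1 and 5.4.1 to 5.4.3. If privacy or local rules bar use of the affected sample, drop that sample's results and keep the patient's other data.

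The PDMP should be aligned at the same time, so that the two lists do not diverge. The cost is one row moved in the SAP and a matching edit to the PDMP. No new data or procedures are needed.
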